24 hours					
30 hours					
36 hours					
42 hours					
48 hours					

Labs:

Times post CPB	Date/Time	Creatinine	Urine Sample
6 hours:			
12 hours:			
24 hours			
48 hours			

Scores:

Times post CPB	Date/Time	AKIN/AKI	Inotropic
6 hours:			
12 hours:			
18 hours			
24 hours			
30 hours			
36 hours			
42 hours			
48 hours			

*Daily chest x-ray

Appendix 3

Neonatal/Infant Pain Scale (NIPS)

(Recommended for children less than 1 year old) A score greater than 3 indicates pain.

Pain Assessment		Score
Facial Expression		
0 - Relaxed Muscles	Restful face, neutral expression	
1- Grimace	Tight facial muscles; furrowed brow, chin, jaw (negative facial expression – nose, mouth brow)	
Cry		
0 - No cry	Quiet, not crying	
1- Whimper	Mild moaning, intermittent	
2 - Vigorous cry	Loud scream; rising, shrill, continuous (Note :Silent cry may be scored if baby is intubated as evidenced by obvious mouth and facial movement)	
Breathing Pattern		
0 - Relaxed	Usual pattern for this infant	
1- Change in breathing	Indrawing, irregular, faster than usual ;gagging, breath	
Arms		
0- Relaxed/Restrained	No Muscular rigidity; occasional random movements of arms	
1- Flexed/Extended	Tense, straight arms; rigid and/or rapid extension, flexion	
Legs		
0- Relaxed/Restrained	No Muscular rigidity; occasional random movements of legs	
1- Flexed/Extended	Tense, straight legs; rigid and/or rapid extension, flexion	
State of Arousal		
0 - Sleeping/Awake	Quiet, peaceful, sleeping or alert, random leg movements	
1- Fussy	Alert, restless and thrashing	

Appendix 4

The AKIN classification/staging system of acute kidney injury

Stage	SCr	UO
1	\uparrow SCr $\geq 26.5 \mu\text{mol/L}$ ($\geq 0.3 \text{ mg/dL}$) or \uparrow SCr $\geq 150\text{-}200\%$ ($1.5 - 2\times$)	$<0.5 \text{ mL/kg/h}$ ($>6 \text{ h}$)
2	\uparrow SCr $>200\text{-}300\%$ ($>2 - 3\times$)	$<0.5 \text{ mL/kg/h}$ ($>12 \text{ h}$)
3	\uparrow SCr $>300\%$ ($>3\times$) or if baseline SCr $\geq 353.6 \mu\text{mol/L}$ ($\geq 4 \text{ mg/dL}$) \uparrow SCr $\geq 44.2 \mu\text{mol/L}$ ($\geq 0.5 \text{ mg/dL}$)	$<0.3 \text{ mL/kg/h}$ (24 h) or anuria (12 h)

Inotrope Score (IS) =

Dopamine dose (mcg/kg/min) + Dobutamine dose (mcg/kg/min) + 100 x Epinephrine dose (mcg/kg/min)

Vasoactive-Inotropic Score (VIS)=

IS + 10 x Milrinone dose (mcg/kg/min) + 10,000 x Vasopressin dose (units/kg/min) + 100 x Norepinephrine dose (mcg/kg/min)

Classification system based on inotropic score

Group[†]	IS or VIS 1st 24 hours	IS or VIS 24–48 hours
1	<10	<5
2	10–14	5–9
3	15–19	10–14
4	20–24	15–19
5	≥25	≥20

[†]Group assignment based on highest support level in either time period.

(Example: Patient with maximum IS 22 in first 24 hours, and 14 in the subsequent 24 hours, would be classified as group 4. Similarly, a patient with maximum IS 10 in the first 24 hours and maximum IS 25 in the second 24 hours would be classified as group 5.)

[name],^{1,2} [name],³ [name],⁴ [name],^{1,2} [name],² Sunkyung Yu, MS,² Christine Gall, MS,⁵ [name],⁴ and Ravi R. Thiagarajan, MD⁶ Vasoactive-Inotropic Score (VIS) is Associated with Outcome After Infant Cardiac Surgery: An Analysis from the Pediatric Cardiac Critical Care Consortium (PC⁴) and Virtual PICU System Registries. Pediatr Crit Care Med. 2014 Jul; 15(6): 529–537.

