The primary objective of this study is to identify whether electroacustimulation is a beneficial anesthesia adjunct in children undergoing procedures on their congenital heart defects. Does it decrease myocardial injury and or need for myocardial support. Differences between the groups Troponin I levels pre-operative and six hours postoperative will be evaluated.

Secondary Objectives:

1) Evaluate the incidence discomfort in the post- operative period.

To evaluate the incidence and severity of pain assessed by using age appropriate West Virginia University Hospital approved nurse guided pain scoring the Neonatal/Infant Pain Scale (NIPS) (children age birth to 2 months) FLACC (2 months to 7 years or unable to communicate, or VAS(age 8-18) every 2 hours for 48 hours post procedure.

2) Determine the incidence of Acute kidney injury (AKI) between these two treatment groups. Acute Kidney Injury will be evaluated by AKIN criteria. Creatinine and urines will be measured at 6, 12, 24 and 48 hours after bypass.

Need for post-operative myocardial support:

To assess the need for myocardial support an inotropic score will be used and compared between the two groups. The Inotropic score will be evaluated every 6 hours for 48 hour between the 2 groups

Study Design:

This is a single site, randomized, blinded, sham controlled, parallel group study to identify whether electroacustimulation is a beneficial anesthesia adjunct in children undergoing procedures on their congenital heart defects.

Study subjects age's birth to eighteen years, undergoing cardiac surgery for their congenital heart lesions will be considered for entrance into the study. The randomized subjects will receive either electrostimulation or sham during their surgery for CHD. Subjects are expected to remain in the hospital 48 hours post procedure. Standard of care blood samples will be obtained pre-operative and post-operative. The only study specific blood sample will be Troponin I levels which will be obtained presurgically after the lines have been placed and a 6 hours post bypass/aortic clamp removal. Urine samples will be obtained pre-surgically after placement of the Foley and every 6 hours post bypass for 48 hours while the Foley catheter is still in place .

Number of Subjects planned:

Approximately 108 patients, over the two years, with randomization of 54 allocated to each group.

- Electroacustimulation (treatment) frequency will be at 2Hz and 100 Hz the amplitude will be 1000mA.

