Group 2: Receive sham electroacustimulation (control) will not have stimulation. Subjects will undergo procedures on their congenital heart defects.

Blind:

The anesthesia provider will be blinded as to whether the electroacustimulation device is actually turned on or not. The research coordinator will hold the blind. The electroacustimulation machine will be placed in an opaque bag to secure the blind. The current is below the threshold to stimulate the muscle so that no movement will be visible. It is also below the sensory threshold so that it will not produce any discomfort in the subjects.

Stimulation/Sham will be continued until the patient is ready for transport to the PICU.

Post-Operative: PICU

Stimulation/Sham will be discontinued.

PICU care givers will be blinded as to which group the patients were randomized.

Subject comfort will be assessed using age appropriate West Virginia University Hospital approved nurse guide pain scoring based on Universal Pain Assessment Tool or the Neonatal/Infant Pain Scale (NIPS) will be recorded in the electronic medical record (EMR) every 6 hours for 48 hours.

The amount of opiate infused, Nausea, Vomiting, and urine output will be assessed every 6 hours for the first 48 hours and recorded in the EMR.

Research blood samples for troponin I will be obtained at 6 hours post surgery. Total amount of 7cc of blood will be

obtained for this study. WVUH lab will process samples.

Research urine samples (.05-2cc) will be collected at 6, 12, 24, and 48 hours after bypass. The urine samples will be stored in a -80 degree freezer and analyzed by ELISA testing at the end of the study for Superoxide dismutase, Neutrophil gelatinase – associated lipocalin (NGAL), WNT4.

AKIN criteria will be used to evaluate AKI every 6 hours. Inotropic score will be recorded every 6 hours.

Daily chest x-ray will be used to assess pulmonary status.

The AKIN criteria, inotropic scores, chest x-ray and creatinine levels, (used for AKIN), are standard of care measurements and the data will be collected for this research project.

An Electrostimulation Documentation Guide has been developed for the staffing. (Appendix A2)

Tool/Instruments to be used in data collection:

Tools and instruments for data collection: secured Excel data base; Neonatal/Infant Pain Scale (NIPS); AKIN stage; Inotropic Scores; RACHS categories (Appendix A3-6).

Variables:

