Predicated on the primary aim, the sample size for this pilot study we used a two-sided two-sample t-test with unequal variance t-test with an alpha level of 0.05 and power of 80%. A morphine equivalent dose of 0.71 mg/kg was used for the control group and 0.57 mg/kg for the acupuncture group. This represents a conservative 20% change between the control and acupuncture group. The standard deviation of the control group was estimated to be 0.3 mg/kg for the control group and 0.2 for the experimental group. **The total estimated sample size is 108 patients, over the two years, with 54 allocated to each group.** Historically, we would have had a potential enrollment and retention of approximately 74 patients per year accounting for a 25% non-consent rate and a 2% drop-out rate. This project is well powered for statistical significance and feasibility for a 2-year study.

Data collection:

The data will be retrieved from the EMR and imported or entered into a secured EXCEL database.

Statistical analysis plan:

For all aims, univariate statistics (e.g. mean, median, standard deviation, min, max and skew) will be used to describe the collected data. Parametric approaches (e.g. t-test, Pearson's correlation, and chi-squared test) will be used when the data satisfy the required statistical assumptions; they will be used to compare the demographic and clinical characteristics between treatment and control. If the distributional assumptions are untenable, then the Mann-Whitney test, Spearman

correlation, and Fisher's exact test will be used. We will use the Box-Cox or the exponential transformation when the absolute value of skew is greater than 0.4.

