Appendix B: Variable descriptions.

Variable	Description	Measurement times	Measurement scale
Outcomes			
Pain score	Age appropriate WVUH approved Nurse guided pain scoring. The pain scale score will be recorded in the electronic medical record.	Every 2 hours for 48 hours	Tool: NIPS score, FLACC score or Visual analog scale Scale: 0-10; 0=none, 10=worst pain
Inotropic score	IS or VIS 1 st 24 hours IS or VIS 24-48 hours	Every 6 hours for the first 48 hours of observation	Group 1-5
Narcotic use	Opiate use will be its own variable as well as a surrogate for pain as comfort will be maintained at a score less than 40% of the max possible score for the pain scoring system used.	Every 2 hours for 48 hours	mcg/kg/hr
Creatinine/Urine	Assessment of AKI-renal complication	Baseline, 6, 12, 24, and 48 hrs post CPB	Creatinine mg/dl Urine ml/kg/hr
Neutrophil gelatinase-associated lipocalin (NGAL)	Renal biomarker-urine sample collected and frozen-renal complication	Baseline, 6, 12, 24, and 48 hrs post CPB	ELIZA
WNT4	Renal Biomarker-urine sample collected and frozen-renal complication	Baseline, 6, 12, 24, and 48 hrs post CPB	ELIZA
AKIN score	Acute kidney injury (AKI)-renal complication	Every 6 hours for the first 48 hours of observation (EMR)	Stage 1-3
Superoxide dismutase	Renal Biomarker-urine sample collected and frozen-cardiac injury-complication	Baseline, 6, 12, 24, and 48 hrs post CPB	ELIZA
Pneumonia	complication	Daily (Chest x-ray)	Indicator: 0=No, 1=Yes
Intubation time	The date and time of intubation as part of surgery prep.	Obtained from patient's EMR	Date and time
Extubation time	The date and time of extubation as part of surgery prep.	Obtained from patient's EMR	Date and time
PICU arrival	The date and time of arrival in the PICU	Obtained from patient's EMR	Date and time
PICU discharge	The date and time of discharge from the PICU	Obtained from patient's EMR	Date and time
Other variables			
Age	Age of the patient	Baseline	In days
Sex	Sex of the patient	Baseline	Indicator: 0=Male, 1=Female
Cardiac defect	Type of CD	Baseline	Diagnosis

Cyanosis	Blueness of skin- based on room air oxygen level less than 90% sat-guide for opiate amount-complication	Baseline	1=yes 2=no
RACHS score	Randomization Guide	Baseline	Categorical: 1 through 6
CPB start time/ Aortic clamp time	Cardiopulmonary bypass (CPB) start time/ Placement of aortic clamp	Obtained from patient's EMR	Date and time

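### The inotropic group needs the maximum score in each 24-hour period, but the plan schedules six-hourly entries from 6 h after bypass and gives no rule for obtaining that maximum

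*Combined protocol and SAP*

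**What the plan says.** **Definition.** The table headed Classification system based on inotropic score gives one set of cut-offs for the first 24 hours and another, 5 points lower, for 24–48 hours. Its footnote states: "Group assignment based on highest support level in either time period". The first example reads: "Patient with maximum IS 22 in first 24 hours, and 14 in the subsequent 24 hours, would be classified as group 4". In Appendix B the measurement scale of the inotropic score is Group 1–5, so this classification is the recorded outcome.

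**Schedule.** Under Objectives: "The Inotropic score will be evaluated every 6 hours for 48 hour between the 2 groups". Under Post-Operative: PICU: "Inotropic score will be recorded every 6 hours". In Appendix B: "Every 6 hours for the first 48 hours of observation". The Scores table of the Documentation Guide is indexed by "Times post CPB" and has eight rows, at 6, 12, 18, 24, 30, 36, 42 and 48 hours. It has no row at 0 h or at PICU arrival.

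**Source.** The PICU section says: "The AKIN criteria, inotropic scores, chest x-ray and creatinine levels, (used for AKIN), are standard of care measurements". The Data collection section adds: "The data will be retrieved from the EMR and imported or entered into a secured EXCEL database".

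**Not stated.** The plan does not say whether an entry is the value at that moment or the highest since the last entry, when the first 24 hours begin, which period a reading at 24 h belongs to, or how the group is derived from the eight entries.

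**The concern.** A classification built on a maximum is only as good as the observation of that maximum. As laid out, the form gives four entries for the first day, the earliest at 6 h. If these are point readings, the stretch from the end of bypass to 6 h is unobserved. That is one quarter of the first day (6/24) if its clock starts at the end of bypass.

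Need for myocardial support is named within the primary objective, and the group is how the plan expresses it. Stimulation stops before transfer to the PICU, and the Background says that its effects dissipate. An early difference in support, if there is one, could therefore fall partly in the unobserved stretch.

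**Working it through.** **1. The plan's own examples.** Day-1 cut-offs are 10, 15, 20 and 25; day-2 cut-offs are 5, 10, 15 and 20. The group is the higher of the two period groups.
- Maxima 22 and 14: day 1 gives group 4 (20–24), day 2 gives group 3 (10–14). Result: 4, as stated.
- Maxima 10 and 25: day 1 gives group 2, day 2 gives group 5. Result: 5, as stated.

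The rule works and does require period maxima.

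**2. Point reading or interval maximum?** Appendix B marks interval quantities explicitly: nausea and vomiting are both defined over a 6-hour window. The inotropic row has no such wording, and each form row has a single date/time cell. A point reading is the natural interpretation, but the text does not settle it.

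**3. Direction of error.** With point readings placed in their correct period, the observed maximum cannot exceed the true one. The group can only be right or too low.

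**4. One child (assumed course).** Score 22 held until 2 h after bypass, then exponential fall: score at 6 h = 22 × 0.5^((6−2)/h), with h the half-life in hours.

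| Half-life | Score at 6 h | Group from readings | Group from true maximum |
|---|---|---|---|
| 6 h | 13.9 | 2 | 4 |
| 12 h | 17.5 | 3 | 4 |
| 24 h | 19.6 | 3 | 4 |
| 48 h | 20.8 | 4 | 4 |

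Over a grid of 48 such courses (peaks 12, 17, 22, 27; held until 1, 2 or 4 h; half-lives 6, 12, 24, 48 h), 27 are read too low, 22 of them by one group and 5 by two. The other 21 are unchanged, including every course with a 48 h half-life.

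**5. Share of children (simulation).** All inputs are assumptions: a lognormal peak with log-SD 0.5, then exponential fall. The true group is the higher of the day-1 group of the peak and the day-2 group of the score at 24 h. The recorded group uses the 6 h reading for day 1, and for day 2 either the 24 h reading (lower figure in a range) or the 30 h reading, if the 24 h one is counted for day 1 (higher figure).

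| Assumed course | Half-life 6 h | 12 h | 24 h |
|---|---|---|---|
| Median 12, falling from 0 h | 64% | 58% | 22–35% |
| Median 12, held until 4 h | 45% | 24% | 8–21% |
| Median 5, falling from 0 h (24 h reading in day 2) | 8% | 8% | 1% |
| Median 12, held until 6 h (24 h reading in day 2) | 0% | 0% | 0% |

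In the first row, the error is two or more groups in 32%, 5% and 0%. With median 12, a fall from 0 h and a 48 h half-life, 5–17% are read too low.

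**6. The 24 h boundary.** A score of 12 at 24 h is group 2 by the day-1 cut-offs and group 3 by the day-2 cut-offs. The boundary matters even when the peak is seen. Take a score of 9 held until 6 h with a 24 h half-life. It is 9 × 0.5^(18/24) = 5.35 at 24 h (day-2 group 2) and 9 × 0.5^(24/24) = 4.5 at 30 h (day-2 group 1). The recorded group is 2 or 1 depending on where the 24 h reading is put.

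**7. Sample size.** The 108 rests on morphine-equivalent dose: (0.3² + 0.2²)(1.960 + 0.842)²/0.14² = 52.06, so 53 per arm by the normal approximation. Welch power at 54 per arm is 80.6%. The inotropic score does not enter.

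**The case against.** The strongest reply is that the plan leaves the derivation open rather than getting it wrong. No text calls an entry a spot value, the scores are standard-of-care data, and the data come from the EMR, so the maximum may already be recoverable. This stands in part: it rules out saying that early peaks are never captured. It does not supply the missing rule, and the form filled in as laid out would not yield the maximum.

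A reader might infer that support peaks around PICU arrival and that children are therefore generally grouped too low. The documents give no data on when support peaks. The form's clock also runs from bypass, so the unobserved PICU time is shorter than 6 h.

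A reader might also infer that the unobserved hours are where a treatment difference is most likely, and hence that the comparison is biased toward no effect. The 120-minute dissipation comes from a dog haemorrhage model. The only inotropic-score evidence in the Background, the adult valve trial with stimulation before surgery, reports lower scores at 12, 24 and 48 hours after ICU arrival, a range that the form largely covers. The schedule is the same in both arms, PICU caregivers are blinded, and the simulation above has no treatment arms. It shows misclassification, not attenuation of an effect.

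Finally, the plan operationalises the primary objective through Troponin I, and the six-hourly series still serves the longitudinal analysis. Both points limit the weight of the issue but do not remove it.

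**Conclusion.** The point holds as a mismatch between an outcome defined by period maxima and a recording schedule that need not contain them. If entries are point readings, some children may be placed in too low a group, and never too high, provided each reading is put in its correct period.

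The size depends on peak level, peak timing and speed of weaning, none of which the documents give. The assumed courses span 0% to about 64%, and neither end should be quoted as an estimate for this trial. The consequence is misclassification common to both arms that may dilute an early difference; a bias toward no effect is not shown. Which period receives the 24 h reading is a convention still to be fixed, not an error to be corrected. The issue deserves a change before analysis, but it does not bear on the sample size.

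**What to change.** - Define time zero for the two 24-hour periods. The form counts from bypass, Appendix B from an undefined start of observation. If the periods start elsewhere than at the end of bypass, the form rows and the periods will not line up.
- Derive the maximum for 0–24 h and for 24–48 h from the time-stamped infusion record in the EMR, starting at PICU arrival, where that record is available. State whether each six-hourly entry is a point value or an interval maximum, and how the group is obtained when only those entries exist.
- Add a PICU-arrival row to the Scores table.
- Assign a reading at exactly 24 h to one period in advance, because the day-2 cut-offs are 5 points lower.
- Keep the six-hourly values for the longitudinal analysis.

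The cost is a few lines in the analysis plan, one form row and a modest amount of extra EMR extraction. No additional patient procedure is needed.

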Appendix A.6

RACHS category 1:

1. Secundum ASD
2. Aortopexy
3. PDA (> 30 days of age)
4. Coarctation (> 30 days of age)
5. PAPVR repair

RACHS category 2:

1. Aortic valvuloplasty (> 30 days of age)
2. SubAS resection
3. Pulmonary valvuloplasty or replacement
4. RV infundibulectomy
5. RVOT augmentation
6. Coronary fistula repair
7. ASD & VSD repair
8. Primum ASD repair
9. VSD repair
10. Tetralogy repair
11. VSD closure with PA band removal
12. Repair of unspecified septa! defect
13. TAPVR repair (> 30 days of age)
14. Glenn shunt
15. Vascular ring surgery
16. A-P window repair

17. Coarctation repair (:5 30 days of age)

18. PA stenosis repair

19. Common atrium closure

20. LV-RA shunt repair

RACHS category 3:

1. AVR

2. Ross procedure

3. LVOT patch

4. Ventriculomyotomy

5. Aortoplasty

6. Mitral valvuloplasty or replacement

7. Tricuspid valvuloplasty or valvectomy or replacement

8. Tricuspid valve repositioning (Ebstein's) (> 30 days of age)

9. Anomalous coronary artery repair with or without intrapulmonary tunnel (Takeuchi)

10. Closure of semilunar valve (aortic or pulmonary valve)

11. RV-PA conduit

12. LV-PA conduit

13. DORV repair with or without RV obstruction

14. Fontan

15. AVSD (complete or transitional) repair with or without valve replacement

16. PA banding

17. Tetralogy with Pulm. Atresia repair

18. Cor triatriatum repair
19. Systemic-Pulmonary artery shunt
20. Atrial switch operation
21. Arterial switch operation
22. Pulmonary artery reimplantation
23. Annuloplasty
24. Coarctation & VSD repair
25. Cardiac tumor excision

RACHS category 4:

1. Aortic valvuloplasty (;;; 30 days of age)
2. Konno procedure
3. Complex defect (Single ventricle) repair with VSD enlargement
4. TAPVR repair (;;; 30 days of age)
5. Rastelli procedure
6. Atrial switch with VSD closure
7. Atrial switch with subpulmonary stenosis repair
8. Arterial switch with PA band removal
9. Arterial switch with VSD closure
10. Arterial switch with subpulmonary stenosis repair
11. Truncus repair
12. Repair of ... or interrupted aortic arch with or without VSD repair
13. Unifocalization ... Tetralogy-PA
14. ...

RACHS category 5:

1. Tricuspid valve repositioning for neonatal Ebstein's (:S 30 days of age)
2. Truncus with Interrupted aortic arch repair

RACHS category 6:

1. Norwood operation
2. ...

Appendix B: Variable descriptions.

Variable	Description	Measurement times	Measurement scale
Outcomes			
Pain score	Age appropriate WVUH approved Nurse guided pain scoring. The pain scale score will be recorded in the electronic medical record.	Every 2 hours for 48 hours	Tool: NIPS score, FLACC score or Visual analog scale Scale: 0-10; 0=none, 10=worst pain
Inotropic score	IS or VIS 1 st 24 hours IS or VIS 24-48 hours	Every 6 hours for the first 48 hours of observation	Group 1-5
Narcotic use	Opiate use will be its own variable as well as a surrogate for pain as comfort will be maintained at a score less than 40% of the max possible score for the pain scoring system used.	Every 2 hours for 48 hours	mcg/kg/hr
Creatinine/Urine	Assessment of AKI-renal complication	Baseline, 6, 12, 24, and 48 hrs post CPB	Creatinine mg/dl Urine ml/kg/hr
Neutrophil gelatinase-associated lipocalin (NGAL)	Renal biomarker-urine sample collected and frozen-renal complication	Baseline, 6, 12, 24, and 48 hrs post CPB	ELIZA
WNT4	Renal Biomarker-urine sample collected and frozen-renal complication	Baseline, 6, 12, 24, and 48 hrs post CPB	ELIZA
AKIN score	Acute kidney injury (AKI)-renal complication	Every 6 hours for the first 48 hours of observation (EMR)	Stage 1-3
Superoxide dismutase	Renal Biomarker-urine sample collected and frozen-cardiac injury-complication	Baseline, 6, 12, 24, and 48 hrs post CPB	ELIZA
Pneumonia	complication	Daily (Chest x-ray)	Indicator: 0=No, 1=Yes
Intubation time	The date and time of intubation as part of surgery prep.	Obtained from patient's EMR	Date and time
Extubation time	The date and time of extubation as part of surgery prep.	Obtained from patient's EMR	Date and time
PICU arrival	The date and time of arrival in the PICU	Obtained from patient's EMR	Date and time
PICU discharge	The date and time of discharge from the PICU	Obtained from patient's EMR	Date and time
Other variables			
Age	Age of the patient	Baseline	In days
Sex	Sex of the patient	Baseline	Indicator: 0=Male, 1=Female
Cardiac defect	Type of CD	Baseline	Diagnosis

Cyanosis	Blueness of skin- based on room air oxygen level less than 90% sat-guide for opiate amount-complication	Baseline	1=yes 2=no
RACHS score	Randomization Guide	Baseline	Categorical: 1 through 6
CPB start time/ Aortic clamp time	Cardiopulmonary bypass (CPB) start time/ Placement of aortic clamp	Obtained from patient's EMR	Date and time
CPB end time/Removal of aortic clamp	Cardiopulmonary bypass (CPB) end time/ removal of aortic clamp	Obtained from patient's EMR	Date and time
Surgery start time	Surgery start time	Obtained from patient's EMR	Date and time
Surgery stop time	Surgery stop time	Obtained from patient's EMR	Date and time
Nausea	Occurrence of nausea within a 6 hour period	Every 6 hours for the first 48 hours of observation (EMR)	Indicator: 0=No, 1=Yes
Vomiting	Number of episodes in a 6 hour period	Every 6 hours for the first 48 hours of observation (EMR)	Count of occurrences
Urine output	AKI	Every 6 hours for the first 48 hours of observation (EMR)	ml/kg/hr
Atelectasis	Graded by number of lobes with atelectasis.	Daily (Chest x-ray)	Count of the number of lobes

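### The inotropic score is left as either of two formulas on a one-per-child 48 h grouping scheduled every 6 hours; the plan should name VIS and analyse its numeric value.

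*Combined protocol and SAP*

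**What the plan says.** - **Which score.** Appendix B (Inotropic score row) allows IS or VIS in both windows; the second entry reads "IS or VIS 24-48 hours". The inotropic score appendix prints both formulas and selects neither. IS sums dopamine, dobutamine and 100 times epinephrine. VIS is "IS + 10 x Milrinone dose (mcg/kg/min) + 10,000 x Vasopressin dose (units/kg/min) + 100 x Norepinephrine dose (mcg/kg/min"). Both share one table of cut-offs.
- **Which scale.** Appendix B gives the scale as groups 1 to 5. The footnote to the classification table states: "Group assignment based on highest support level in either time period". The cut-offs differ by window: group 1 is below 10 in the first 24 h and below 5 in the second.
- **Which schedule.** Under the protocol heading on post-operative myocardial support: "The Inotropic score will be evaluated every 6 hours for 48 hour between the 2 groups". The Post-Operative: PICU section also has the score recorded 6-hourly. The Documentation Guide has one Inotropic column with eight post-bypass rows (6 to 48 hours). Its baseline block does not list the score.
- **Which analysis.** The Statistical analysis plan compares arms on the change from baseline to 48 hours (a t-test for continuous outcomes, logistic regression with a contrast of the two times for categorical ones). It then describes trends with a mixed model.
- **Its role.** The Primary Objective asks about myocardial injury and about the need for support, but the only measure it names is troponin I. The inotropic score has its own heading after the Secondary Objectives.

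**The concern.** Three choices are open or in conflict: the formula, the quantity analysed (6-hourly number or 48 h group), and the comparison between arms. With the formula open, two children on identical drugs could be scored differently, or the formula could be settled after the data are seen. With the quantity open, the stated scale does not fit the stated schedule or either planned analysis. If the five groups are what is tested, differences within a group disappear. This is the plan's only scored measure of myocardial support, so these choices decide how that part of the objective is answered.

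**Working it through.** **1. The plan's own figure.** No distribution, effect or power is given for the inotropic score. The sample size rests on opioid dose: "A morphine equivalent dose of 0.71 mg/kg was used for the control group and 0.57 mg/kg for the acupuncture group", with SDs "estimated to be 0.3 mg/kg for the control group and 0.2 for the experimental group". The difference is 0.71 − 0.57 = 0.14. By normal approximation, n per arm = (1.96 + 0.84)² × (0.3² + 0.2²) / 0.14² = 7.85 × 0.13 / 0.0196 ≈ 52.1, so 53. The exact Welch calculation gives power 0.799 at 53 and 0.806 at 54, so 54 per arm is confirmed ("The total estimated sample size is 108 patients, over the two years, with 54 allocated to each group"). This says nothing about power for the inotropic score; only the 54 per arm is carried forward.

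**2. IS against VIS.** These are arithmetic illustrations in the listed units, not statements about what children receive.

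| Inputs | IS | VIS |
|---|---|---|
| Milrinone 0.5 | 0 | 10 × 0.5 = 5 |
| Epinephrine 0.05, milrinone 0.5 | 100 × 0.05 = 5 | 5 + 5 = 10 |
| Milrinone 0.75, vasopressin 0.0005, norepinephrine 0.1 | 0 | 7.5 + 5 + 10 = 22.5 |

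In the last row IS gives group 1. VIS gives group 4 if reached in the first 24 h (20–24) and group 5 if reached at 24–48 h (20 or more).

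**3. Scale against schedule and analysis.** The group is the worse of two window maxima, so each child has one value per 48 h. The table's two worked examples (maxima 22 then 14, group 4; 10 then 25, group 5) follow this rule. One value has no separate baseline and 48 h readings to contrast, and no trajectory for a mixed model. If the numeric score was meant, the mixed model works, but a change from baseline still cannot be computed because no baseline score is scheduled.

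**4. Power, groups against numbers.** All distributional inputs are assumptions:

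- 54 per arm; lognormal VIS, log SD 0.7; 30% reduction with treatment.
- The 24–48 h level is 0.6 times the first-window level, with correlation 0.7.
- Groups use the plan's cut-offs; two-sided Mann-Whitney test at 0.05.

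| Control median, first-window VIS | Power, 48 h maximum VIS | Power, groups 1–5 | Loss (points) |
|---|---|---|---|
| 5 | about 75% | about 49% | 26 |
| 8 | about 75% | about 65% | 10 |
| 12 | about 75% | about 72% | 3 |

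The second window matters because its cut-offs are lower. Ignoring it, group power falls to 34%, 54% and 63% at the same medians.

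A second set of runs fixed the effect at 0.56 log SD and used log SD 0.5 or 0.8. At a control median of 5, 67–81% of control children were in group 1 and the loss was 23–37 points. At 8, 43–47% were in group 1 and the loss was about 8–10 points. At 12, 18–24% were in group 1 and the loss was about 2–4 points. The loss therefore follows the share of children in group 1.

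**The case against.** The best defence is that this is a small specification gap. The 6-hourly entry sits in the measurement-times column and can be read as the raw readings from which a 48 h maximum is taken. The form already has eight cells, so nothing need be lost at collection. The plan prints the full VIS formula, which covers all six listed drugs. The five-level classification is published, so testing a number instead is partly preference. The power figures use an unadjusted rank test, whereas the plan names logistic regression for categorical outcomes and will at least assess a RACHS adjustment.

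Much of this stands, and it limits what can be claimed:

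- A reader might infer that the plan's score misses most support. That holds only if IS is used, and then only for children on drugs outside IS.
- A reader might infer that 6-hourly data will not exist. The protocol and the form provide for them.
- A reader might blame the grouping for the failed change score. The missing baseline defeats it for numeric VIS equally.
- The simulation compares two codings under one test; it does not estimate the power of the planned model.

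What does not stand is that the text resolves itself. Nothing says which formula goes in the cell, whether the cell holds a number or a group, or which of these is analysed.

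**Conclusion.** The point holds as a mismatch among score, scale, schedule and analysis, and it should be corrected before the data are unblinded. The choice between IS and VIS is open. The listed scale gives one value per child and fits neither planned analysis. The baseline-to-48 h change cannot be computed for this outcome on either reading.

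A reader might go further and say that the plan loses substantial power. The documents do not support that: they give no IS or VIS distribution and no expected effect. Under the stated assumptions the loss is about 26, 10 and 3 points at control medians of 5, 8 and 12, and it is large only if most children fall in group 1. Eligibility includes RACHS category 1 procedures and coarctation, so children needing little support may be enrolled, but their share is not stated. The lognormal model also has no zero scores; children with no support would be tied under either coding.

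A reader might also call this half of the primary endpoint. The objective's wording mentions support, but troponin I is the only measure named there. The score is best described as a supporting outcome within the primary objective's wording.

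**What to change.** 1. In Appendix B and the inotropic score appendix, name VIS as the score for every child.
2. State that the Inotropic cells of the Documentation Guide hold the numeric VIS at each of the eight times.
3. In the Statistical analysis plan, compare the maximum VIS over 0–48 h between arms by a rank test, or by log(VIS + 1) adjusted for RACHS. Choose one in advance.
4. Use the 6-hourly VIS values in the mixed model.
5. Drop the baseline-to-48 h change for this outcome.
6. Keep groups 1 to 5 as a descriptive table.
7. Describe the score as a supporting outcome.

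The cost is a change of wording. The numeric score has to be computed anyway to assign a group, and the form already has the cells. The downside is that the published grouping is no longer the tested outcome; the descriptive table keeps it available for comparison with other work.
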